## I. PURPOSE OF THE STUDY AND BACKGROUND

Cervical cancer is among the most preventable forms of cancer. Implementation of widespread cervical cancer screening has resulted in a tremendous decrease in the incidence of cervical cancer in the United States and stands as a cornerstone of preventive health efforts. Still, only 80.7% of U.S. women aged 21 – 65 years report adherence to U.S. Preventive Services Task Force (USPSTF) cervical cancer screening recommendations. This rate is far below the *Healthy People 2020* target of 93%. The group identified as most likely to be non-adherent with recommended screening protocols are patients who use the emergency department (ED) for their usual source of care. **The overall goal of the proposed study is to pilot two brief behavioral interventions aimed at improving adherence to cervical cancer screening among ED patients.** The results of this pilot will prepare our interdisciplinary team to successfully compete for NIH funding to scale up the evaluation of the proposed interventions. In order to achieve this goal, we propose to leverage an existing parallel service program in the high volume general population setting of the URMC ED to accomplish the following specific aims:

**Specific Aim 1:** Conduct a randomized pilot trial comparing the efficacies of two structured behavioral interventions in promoting adherence of women aged 21 – 65 to USPSTF cervical cancer screening recommendations: A. Screening & referral and, B. Screening, brief mobile technology-based intervention grounded in the Theory of Planned Behavior (TPB), & referral.

**Hypothesis 1A/1B:** The proposed interventions will improve adherence to USPSTF recommendations at follow-up over baseline levels. Rates of adherence will be greater after Intervention B compared to A.

**Specific Aim 2:** Identify predictors of adherence and non-adherence to USPSTF recommendations at baseline to inform the refinement of the proposed interventions.

[figure not shown]
**Hypothesis 2:** Lower baseline rates of adherence will be identified among ethno-racial minorities, as well as among women with less education, without a usual source of care, and with greater barriers to care.

**Specific Aim 3:** Collect qualitative feedback on perceptions of the interventions to inform their refinement.

[figure not shown]
## II. STUDY DESIGN

**a. Screening, Enrollment, & Randomization.** The proposed pilot study will utilize a randomized, prospectively collected, convenience sample and a short-term longitudinal design. Our approach is summarized in Figure 1 and detailed below. EDRAAs will use the EPIC eRecord system to screen adult patients that are registered in the ED at URMC for eligibility over a four-month period. Inclusion criteria will include: female, age 21 – 65 years. Exclusion criteria will include past hysterectomy with cervical removal, known infection with HIV (as screening recommendations for women with HIV differ from the general population), inability to consent (e.g., lacking decisional capacity, intoxicated, or in distress), non-English speaking, or lack of text-capable mobile phone and/or inability to use text function. Eligible women will then be approached by a representative of the EDRA program who will read a brief script describing the study and inviting the patient to enroll. Consent documentation will be completed for all enrollees. Based on previous studies with a similar level of patient involvement utilizing our EDRA program, we anticipate an enrollment rate of >85% of eligible participants, such that approximately 530 women will be approached.

**Figure 1. Project Workflow**

After consent, enrollees will complete a ~10-minute computer-adaptive questionnaire, administered at the bedside on a tablet computer by the EDRA to determine adherence to current USPSTF recommendations for cervical cancer screening. The REDCap adaptive screening tool used will be identical to that which was used to gather our preliminary data. The enrollment process will categorize study participants into three groups: adherent, uncertain, or non-adherent (Figure 2). Women found to be adherent will be notified and their participation will conclude (i.e. no follow-up will be performed). Women found to be in the uncertain or non-adherent groups will then be randomized into one of two intervention conditions. Randomization will be automated in the REDCap survey instrument. All women found non-adherent will be referred to their usual care provider. If the patient does not have a usual provider of women's healthcare, she will be referred to UR WHP to receive appropriate screening. [name] (co-I) will maintain an expedited referral pathway to UR WHP for these subjects. [name] or one of the other health care providers at WHP will conduct the screening test. Women for whom adherence is uncertain (e.g. unsure, unable to remember) will be referred to their usual care provider or to UR WHP to confirm their adherence status. If, upon follow-up, the patient was confirmed adherent, she will be retroactively classified as adherent at baseline (though her uncertain status at screening will be retained in the dataset for potential secondary analyses). If confirmed non-adherent, the patient will be retroactively classified as non-adherent at baseline (with initial uncertainty retained). If the patient did not contact a provider to confirm adherence status (and did not remember her status in the 150 day interim), she will remain classified as uncertain.

**b. Description of Interventions.** The proposed study pilots two interventions aimed at improving adherence to guidelines by encouraging screening outside of the ED. **Intervention A** only involves screening for adherence status and referral of uncertain and non-adherent patients for screening and/or confirmation of status and screening. **Intervention B** follows the Screening, Brief Intervention, and Referral to Treatment (SBIRT) model popularized in the substance use literature in the ED . The three components of the TPB intervention will be delivered via a series of text messages to mobile phones. Patients will receive a total of three text messages at 30-day intervals between the ED index visit and telephone follow-up survey at

150 days. Each text message will include a statement directed towards one of the TPB predictors of behavioral change intentions (Table 1) accompanied by a reminder to schedule cervical cancer screening with their primary provider or the WHP. Attitudes regarding cervical cancer screening will be addressed by emphasizing its efficacy for preventing morbidity.

Table 1 – Theory of Planned Behavior Texts to Participants in Intervention B

Element of the TPB	TPB portion of text	Scheduling portion of text
Attitudes about Screening	“Regular screening for cervical cancer is an extremely effective way to prevent cancer or identify early stages of cancer that can be effectively treated”	
Subjective Norms about Screening	“Over 80% of women across the country stay up-to-date with cervical cancer screening guidelines.”	Schedule cervical screening by calling your usual women’s health provider at {Participant-specific phone number} or with UR Women’s Health Practice at [contact]
Perceived Behavioral Control over Obtaining Screening	“Pap tests are available, without cost to you, at your women’s health provider or at the UR Women’s Health Practice.”	

Subjective normative beliefs about screening will be addressed by emphasizing the preponderance of adherence to guidelines in the population. Perceived behavioral control over obtaining cervical screening will be addressed by discussing the accessibility and negligible financial burden of Pap tests. Women who have their own women’s health providers will be instructed to follow-up with these providers or utilize UR WHP, whichever they prefer. To facilitate patient follow through, the message will include hyperlinks to the telephone numbers of the patient’s women’s health care provider (if known) and the WHP.

**c. Follow Up.** All enrollees in the non-adherent and uncertain groups will receive a follow-up call at 150 days (Figure 3). The project coordinator will contact each of these participants by telephone for a brief REDCap questionnaire to determine if they underwent screening, if they learned that they did not require screening, and what barriers they perceived in getting screened or clarifying their adherence. Qualitative feedback regarding perceptions of the interventions will also be solicited from study participants in order to refine the interventions for future study. Relevant domains of feedback will include challenges to adhering with screening guidelines, comfort level with the intervention content discussed in the ED, which TPB message(s), if any, were perceived as most generative of intention to engage in cervical cancer screening, and participant recommendations for intervention revision. Telephone numbers will be confirmed in the ED during enrollment by the EDRA performing the enrollment (e.g., calling patient’s phone to be certain the number is correct), and up to 3 calls will be made to each of these patients to limit unnecessary attrition.

Study team members will use the EPIC medical record to confirm self-reported screening activities among the subjects successfully contacted at follow-up and who report a women’s health provider associated with UR Medicine. No confirmation will be sought among subjects reporting cervical screening with providers outside of the UR Medicine system.

A limited medical record review will be conducted for all enrolled subjects to determine cervical cancer screening activities and results through providers associated with UR Medicine in the prior 5 years. These data will be compared to self-reported screening activities to demonstrate the validity of the study procedure used in the current study. These data will also be used to determine the extent to which subjects are aware of their suggested screening schedules based on history (e.g., abnormal Pap test results, positive high-risk HPV test).

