### **XI. DATA ANALYSIS**

**a. Plan of Analysis.** Based on previous research and our preliminary data, we anticipate  $\geq 18\%$  of patients will be non-adherent to screening guidelines. As such, we will enroll 450 patients to identify  $\geq 90$  non-adherent patients. To test **Specific Aim 1 - Hypotheses 1A/1B**, we will use (a) a one sample test of improvement in adherence at follow-up and (b) a two-sample comparison of post-intervention adherence across intervention conditions. These analyses will allow us to establish preliminary effect sizes for powering the subsequent NIH submission. The first test will compare % adherent at follow-up against a null value of 15% improvement (i.e., % of non-adherent subjects who would become adherent over 150 days without intervention). We think this is an unrealistically high null value, but it was chosen to avoid overestimating the impact of the study interventions. Using this null value, a one-tailed test with  $\alpha=0.05$ , and  $\geq 90$  non-adherent subjects across conditions, we will have power of 0.80 to observe improvement as small as 10% over the null (40% relative improvement). The second test will use  $\chi^2$  to compare conditions. Given a one-tailed test with  $\alpha=0.10$  and 45 non-adherent subjects in each condition, we will have power of 0.70 to observe a difference as small as 24% in adherence at follow-up. More importantly, we will establish a 95% confidence interval around the overall improvement rate (across conditions) with  $\leq 10.4\%$  margin of error and intervention specific rates of improvement with  $\leq 14.8\%$  margin of error. These intervals will allow us to calculate power for the subsequent trial under expected, ideal, and worst-case scenarios. Patients lost to follow-up will be considered intervention failures (i.e. non-adherent) in accordance with intention-to-treat principles. In order to test **Specific Aim 2 - Hypothesis 2**, we will use hierarchical, multinomial logistic regression to predict adherence at baseline. Given our sample size and an expected adherence rate of 0.80, at  $\alpha=0.05$ , we will have power  $\geq 0.70$  to observe odds ratios as small as 1.33. Any covariates demonstrating a  $p$ -value  $\leq 0.10$  will be addressed when refining the interventions for the subsequent NIH trial. **Specific Aim 3** is focused on the qualitative feedback data collected at the 150-day follow-up call. Qualitative data analysis of the feedback data will include open and axial coding under Grounded Theory principles examined in the context of subject demographic characteristics. The codes/concepts that emerge from these data will be examined in the context of the demographic characteristics of the subjects providing feedback. Results will then be used to refine the intervention protocols for the subsequent efficacy trial.

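### The main Aim 2 outcome appears to be a baseline label completed from 150-day follow-up, so its ascertainment can depend on two Hypothesis 2 predictors; the effect falls mainly on the uncertain-versus-adherent contrast

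*Combined protocol and SAP*

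**What the plan says.** All references are to the combined protocol and SAP.

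- **Aim 2 (section I, Purpose of the Study and Background):** "Identify predictors of adherence and non-adherence to USPSTF recommendations at baseline". Hypothesis 2 expects lower baseline adherence among, among others, women "without a usual source of care, and with greater barriers to care".
- **Classification in the ED (section II.a, text under Figure 1):** "The enrollment process will categorize study participants into three groups: adherent, uncertain, or non-adherent". This is done by bedside questionnaire. Then "Women found to be in the uncertain or non-adherent groups will then be randomized into one of two intervention conditions".
- **Later relabelling (same place):** an uncertain woman who is confirmed adherent at follow-up is relabelled: "she will be retroactively classified as adherent at baseline". The mirror rule applies to one confirmed non-adherent. The condition for staying uncertain begins "If the patient did not contact a provider to confirm adherence status" and also requires that she did not recall her status within the 150 days.
- **Role of the ED label:** for the woman confirmed adherent, "her uncertain status at screening will be retained in the dataset for potential secondary analyses"; for the one confirmed non-adherent, the initial uncertainty is likewise kept.
- **Analysis (section XI.a):** "we will use hierarchical, multinomial logistic regression to predict adherence at baseline". Covariates with p≤0.10 are to be taken up in revising the interventions for the next trial.

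Neither XI.a nor XI.b says which of the two labels Aim 2 uses, and neither plans a sensitivity analysis of the relabelling for Aim 2.

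**The concern.** A baseline outcome should be fixed by information collected in the same way for everyone. Here a woman's final class depends on whether she reached a provider, or remembered, after she was randomised. A woman with a usual provider and few barriers has an easier route out of the uncertain class. The plan recognises this link: the 150-day call (section II.c) asks about barriers to clarifying adherence as well as barriers to being screened.

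If resolution differs in this way, women without a provider accumulate in the residual uncertain class even when they were no more uncertain in the ED. The multinomial model would then show an association between provider status and class that arose after baseline. Under the p≤0.10 rule, that association could be carried into the redesign of the interventions as a baseline predictor.

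**Working it through.** **The plan's own Aim 2 figure.** The only one is power of at least 0.70 for an odds ratio (OR) of 1.33, with 450 women, adherence 0.80 and α=0.05. Hsieh's formula for one standardised continuous predictor is power = Φ(ln OR × √(n p(1−p)) − z). Here ln 1.33 × √(450×0.8×0.2) = 0.285 × 8.485 = 2.42. Power is Φ(2.42−1.645) = 0.78 one-sided and Φ(2.42−1.96) = 0.68 two-sided. Sidedness is not stated for Aim 2 and the one-sided reading meets the claim. The point below does not rest on this figure.

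**How many women are uncertain.** The documents give no rate. If the 80% adherent and the minimum 18% non-adherent in XI.a are shares at screening, 100−80−18 = 2% remain, or 0.02×450 = 9 women. The target of 90 non-adherent out of 450 (20%) would leave none. Shares of 5% and 10% are shown only as a range.

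**Assumptions.** ED class is unrelated to provider status, so every true OR is 1. In the ED, 80% are adherent, a share u is uncertain and the rest are non-adherent. 30% have no provider. Half of resolved women prove adherent. A share r of uncertain women is resolved: 60% with a provider, and 20% or 40% without. None of the resolution rates, the 30% or the one-half comes from the documents.

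**Expected shares after relabelling.** Adherent = 0.80 + 0.5ru; non-adherent = 0.20 − u + 0.5ru; uncertain = u(1−r). At u=0.02:

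| | Adherent | Non-adherent | Uncertain |
|---|---|---|---|
| Provider (r=0.6) | 0.806 | 0.186 | 0.008 |
| No provider (r=0.2) | 0.802 | 0.182 | 0.016 |

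- Uncertain v adherent, no provider v provider: (0.016/0.802)/(0.008/0.806) = 2.01.
- Non-adherent v adherent, no provider v provider: (0.182/0.802)/(0.186/0.806) = 0.98.
- Adherent v rest, provider v no provider: (0.806/0.194)/(0.802/0.198) = 1.03.

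The first OR is close to (1−0.2)/(1−0.6) = 2.0 at any u. With 40% resolved among women without a provider it is about (1−0.4)/(1−0.6) = 1.5. If resolution is equal in both groups, or if the ED class is used, all three are 1.00.

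**False flags at p≤0.10.** Simulation with 450 women and 4,000 replicates; Woolf test with 0.5 added to each cell; half of resolved women adherent:

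| Uncertain in ED | ED class, uncertain v adherent | Relabelled, uncertain v adherent, 60% v 20% | Same, 60% v 40% | Relabelled, non-adherent v adherent, 60% v 20% | Relabelled, adherent v rest, 60% v 20% |
|---|---|---|---|---|---|
| 2% | 6% | about 17% | about 9% | 9% | 9–10% |
| 5% | 8–9% | about 33% | 17–18% | 9% | 11% |
| 10% | 8–9% | about 52% | 25% | 11% | 15% |

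The median OR for non-adherent v adherent ran from about 1.0 down to 0.88, so any drift goes against Hypothesis 2. If 80% of resolved women are adherent, the adherent-v-rest flag rate at 10% uncertain rises to 22–24%.

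**How few women this rests on.** At 2% uncertain, 0.3×9 = 2.7 have no provider and 6.3 have one. After relabelling at 60% v 20%, 2.7×0.8 = 2.2 and 6.3×0.4 = 2.5 remain uncertain.

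**The case against.** **The contrast most affected is not the one that Hypothesis 2 names.** The hypothesis concerns rates of adherence, and Aim 2 names adherence and non-adherence. This stands. A reader might infer that the Aim 2 findings on provider and barriers would be spurious in general. The calculations do not support that: adherent v non-adherent stays near the nominal 10%, and adherent v rest moves modestly unless the uncertain group is large. A three-class model does report the uncertain contrast, however, and the p≤0.10 rule has no exception for it.

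**The plan's figures point to few uncertain women.** This also stands. The results at 5% and 10% have no support in the documents and should not be read as forecasts.

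**Use of the rewritten label is inferred.** A reader might take it as stated; it is not. But the relabelled class is the one called baseline and the ED class is put aside for possible secondary use. If the sponsor meant otherwise, the text still needs a sentence saying so.

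**The relabelling recovers true status.** Correct. Having a provider does not alter whether a woman was up to date in the ED, and the rule corrects some missing knowledge. The fault is that the correction is selective. Differential resolution is plausible but not established: uncertain women may also be referred to the UR Women's Health Practice, and recall alone can resolve status. The documents also do not say when the barriers predictor is measured.

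**The Intervention B texts.** A reader might infer that texts prompting provider contact bias the predictor associations as well. Arm is randomised and so independent of baseline predictors; by itself it creates no such association.

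**Conclusion.** The concern holds as a matter of outcome ascertainment. On the natural reading, the main Aim 2 label is completed selectively from events after randomisation, and that selection can depend on usual source of care and barriers.

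The size depends on assumptions. With resolution of 60% v 20%, the uncertain-versus-adherent OR is about 2 when the truth is 1. The false-flag rate is then about 17% at the 2% uncertain share that the plan's figures suggest, if they are screening shares, and more if the group is larger. With 60% v 40% and 2% uncertain, it does not exceed the nominal 10%.

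This is a pilot. No safety conclusion depends on the Aim 2 model, and the Aim 1 comparison is a separate question. The correction is worth making because it is cheap and removes the dependence from the main model, not because Aim 2 as a whole would be misleading.

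**What to change.** In section II.a (text under Figure 1) and in XI.a, state that the main Aim 2 outcome is the three-class status assigned by the ED questionnaire at enrolment, before any follow-up information. Report the model with the reclassified label as a sensitivity analysis. The over-referral analysis in XI.b can go on using the reclassification unchanged.

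The five-year record review in section II.c should not be used to resolve uncertain women for the main model. It sees only UR Medicine providers, so resolution would again depend on provider status.

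The cost is about one sentence in each section and no new data, since the ED status is already retained. The downside is that more women stay uncertain in the main model, and some true baseline statuses learned later contribute only to the sensitivity analysis.

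### Aim 1 does not say whether its non-adherent women are classed at the index visit or by the post-randomisation reset; the reset would push the pooled improvement rate upward

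*Combined protocol and SAP*

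**What the plan says.** Section II.a (text under Figure 1) sorts enrollees into adherent, uncertain and non-adherent, and ends participation for the adherent. Of the rest it says: "Women found to be in the uncertain or non-adherent groups will then be randomized into one of two intervention conditions".

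It then gives three rules for a woman who was uncertain:
- Confirmed adherent: she becomes adherent at baseline, "though her uncertain status at screening will be retained in the dataset for potential secondary analyses".
- Confirmed non-adherent: "If confirmed non-adherent, the patient will be retroactively classified as non-adherent at baseline (with initial uncertainty retained").
- No provider contact and no recollection by day 150: "she will remain classified as uncertain".

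Section II.b describes the Intervention B texts, each "accompanied by a reminder to schedule cervical cancer screening with their primary provider or the WHP". At the day-150 call (II.c) women are asked "if they underwent screening, if they learned that they did not require screening".

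Section XI.a sizes the one-sample test on at least 90 non-adherent subjects and the two-sample test on "45 non-adherent subjects in each condition". It gives more weight to the 95% interval for the pooled improvement rate than to the tests, and will use the intervals to power the next trial. Women lost to follow-up count as failures. Uncertain women are not mentioned. Section XI.b uses reclassification for the over-referral rate. Figures 2 and 3, to which II.a and II.c refer, are not shown in the text available.

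**The concern.** An analysis set should be fixed by what is known at randomisation. Here a label called baseline can be settled up to 150 days later, mainly by provider contact. That contact is the usual way to get screened, so it is close to the outcome itself, and the Intervention B texts prompt it.

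If Aim 1 uses the reset label, an uncertain woman who acts and is found overdue enters the denominator, often already a success. One who does nothing, and is reached at day 150, stays uncertain. The failure rule in XI.a names women lost to follow-up and does not clearly cover her. Removing only women who were not screened can only raise the observed rate. The quantity most exposed is the pooled improvement rate, which XI.a ranks above the tests.

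**Working it through.** **1. The plan's own figures.** Inputs from XI.a: null 15%, alternative 25%, n = 90, one-sided 5%.
- Power by normal approximation: Φ[(0.10 − 1.645·√(0.15·0.85/90)) / √(0.25·0.75/90)] = 0.798. The stated 0.80 reproduces. The exact test rejects at 20 of 90, with size 4.3% and power 76.4%.
- Pooled margin: 1.96·√(0.25/90) = 10.3 points, within the stated 10.4.

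So the pooled interval is sized on the same 90 women. The figures do not show which label defines them.

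**2. Pooled rate under the reset label.** Assumptions, none from the documents: 90 women non-adherent at the index visit; U further women who are uncertain but truly non-adherent; the same true screening rate p in all; every screened woman is also confirmed; a proportion s of confirmed women are screened. The proportion confirmed is then c = p/s, and

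observed rate = (90p + Up) / (90 + Up/s).

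With all women kept, the denominator is 90 + U and the rate is p. Since c is at most 1, the observed rate is never below p.

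At p = 25% with no loss:

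| U | s = 0.3 | s = 0.5 | s = 1.0 |
|---|---|---|---|
| 10 | 25/98.3 = 25.4% | 25/95 = 26.3% | 25/92.5 = 27.0% |
| 20 | 27.5/106.7 = 25.8% | 27.5/100 = 27.5% | 27.5/95 = 28.9% |
| 30 | 30/115 = 26.1% | 30/105 = 28.6% | 30/97.5 = 30.8% |

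Enumerating over the random denominator gives the same values, except 30.7% in the last cell. Coverage of the Wilson 95% interval for the true 25% is 95.0% with the fixed 90. For s from 0.5 to 1 it is 92-94%, 85-91% and 74-86% at U = 10, 20 and 30. For s = 0.3 it stays at 93.8-94.6%.

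**3. Conditions that weaken it.**
- *Loss, counted as failure.* With 10% loss the rate with all women kept is 0.25·0.9 = 22.5%, seen as 23.6-27.0% for s from 0.5 to 1. With 20% loss it is 20.0%, seen as 20.8-23.5%.
- *Remembering.* Suppose half of the women who make no contact recall their status (assumed). The mildest case (U = 10, half of contacting women screened) has 0.5 + 0.5·0.5 = 75% entering: 25/97.5 = 25.6%. The strongest (U = 30, all contacting women screened) has 0.25 + 0.75·0.5 = 62.5% entering: 30/108.75 = 27.6%.
- *Unresolved women kept as failures.* The denominator is 90 + U, and there is no shift.

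**4. The one-sample test.** At a true 15%, with s from 0.5 to 1, the size of the exact test is 7-24% with no loss, 2.5-9.2% with 10% loss and at most 2.5% with 20% loss. With unresolved women kept and no loss it is 3.2-3.9%.

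**5. Between arms.** Take 45 women plus 10 uncertain women per arm, with 25% of the 45 screened (11.25). In one arm 20% of uncertain women are confirmed and 90% of those screened; in the other, 60% and 30%. Both arms gain 1.8 successes, so the true rates are equal at 13.05/55 = 23.7%. The reset label shows 13.05/47 = 27.8% against 13.05/51 = 25.6%. Swapping the patterns reverses the sign.

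**The case against.** The strongest reply is that Aim 1 may never have been meant to use the reset class. Section XI.a enrols 450 women in order to identify at least 90 who are non-adherent, and II.a says the screening tool is the one that produced the preliminary data. That fits a class fixed at the index visit. A reader might infer the opposite from the phrase on secondary analyses, as if the initial status were kept only for those. The text does not say only, and the phrase belongs to women confirmed adherent; for those confirmed non-adherent, II.a merely says the uncertainty is retained. The reset label may serve Aim 2 or over-referral, and the missing figures might settle the matter. This stands: use of the reset class in Aim 1 is one possible reading.

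Second, XI.a invokes intention-to-treat, which argues against dropping randomised women. That is fair as a principle, but its stated rule covers lost women, not those reached and unresolved.

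Third, the larger shifts need high screening among confirmed women and little loss. This also stands, and XI.a itself calls the 15% null unrealistically high, so an inflated one-sample test should not be the headline.

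What remains is that II.a states a rule that changes a baseline class after randomisation, and XI.a does not keep that rule out of Aim 1.

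**Conclusion.** The Aim 1 analysis set is not defined in the visible text, and one of the two readings selects it by behaviour after randomisation. On that reading the pooled improvement rate is pushed upward relative to keeping every truly non-adherent woman in the denominator. With 10 to 30 truly non-adherent uncertain women, no loss and 50-100% of confirmed women screened, a true 25% appears as about 26-31%. With 30% screened the shift is 0.4-1.1 points, and with unresolved women kept as failures it is zero. All these inputs are assumed, because the documents give no number of uncertain women.

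Two stronger conclusions are tempting and not supported. One is that the plan is shown to be biased; that needs the reset reading, which is not established. The other is that Intervention B is favoured; the sign depends on how confirmation and screening differ by arm, and it can go either way. The point should be fixed before analysis. Confidence is medium.

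**What to change.** In II.a and XI.a:
- Define the Aim 1 primary set as women recorded non-adherent in REDCap before randomisation, with no retroactive change.
- Report women uncertain at the index visit separately by arm, all in the denominator, with unresolved and lost women counted as failures.
- Keep the reclassified label for over-referral, Aim 2 or a sensitivity analysis.
- State that a woman who learns she was already up to date is an over-referral, not an improvement. Section XI.b reports such women, but XI.a does not say how they count.

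No new data are needed, since the initial status is already retained. The cost is a slightly smaller set: the pooled margin is 10.3 points at n = 90, against 10.2 to 9.6 at the 92 to 105 women of the scenarios with s from 0.5 to 1.

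Women classed non-adherent at the index visit who were in fact up to date will dilute the rate. That is not a cost of fixing the label: the reset rule touches only uncertain women, so these women stay in under either reading. An optional sensitivity analysis could remove them using the review in II.c ("A limited medical record review will be conducted for all enrolled subjects"). It does not depend on a woman contacting a provider, but it covers UR Medicine providers only.
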